Implementation of a prehabilitation program will be feasible and will improve clinical status.

SPECIFIC AIMS

We propose to pilot (N=20) and assess a new prehabilitation program for frail surgical oncology patients. We will:

1. Assess feasibility. We will:
 - a. Evaluate adherence through analysis of patient maintained exercise logs.
 - b. Assess self-efficacy by evaluating the relationship between pre-program self-efficacy score and adherence.
 - c. Assess patient satisfaction and barriers to adherence through a post prehab program survey.

2. Assess clinical impact. We will:
 - a. Evaluate health-related quality of life before and after participation in the prehabilitation program.
 - b. Evaluate frailty before and after participation in the prehabilitation program.

METHODS

Study Design: Prospective cohort study

This longitudinal study will be a prospective, non-randomized, within-subject design focused on patients diagnosed with complex gastrointestinal (GI) cancer evaluated and treated at Maine Medical Center by the Surgical Oncology Service. All subjects who meet the inclusion criteria will be offered the opportunity to be enrolled; these recruitment efforts will cease when planned enrollment is complete. Participants will complete a prehabilitation exercise program through the Thinkific platform. Data on frailty, quality of life, self-efficacy and adherence will be collected through surveys and patient maintained exercise logs.

Study Population

Participants will be selected from the population of patients at the MMC Surgical Oncology Clinic. Patients at this clinic are being evaluated for surgical treatment of oncologic diseases such as colorectal or pancreatic cancer. Under normal circumstances, patients are seen for an initial consultation where a treatment plan is created. Patients either have surgery or chemotherapy up front. If the patient has surgery as the first treatment, the surgery is scheduled at that initial appointment. If the patient has chemotherapy before surgery, they will return for at least one more appointment after completion of chemotherapy. Their surgery is scheduled at this follow-up appointment. This process can span anywhere from 4 weeks to 6 months.

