After the account is created, participants will complete two electronic baseline surveys on an in room device during this initial clinic visit: the 36-Item Short Form Survey (SF-36) and the Self-Efficacy for Home Exercise Programs Scale (SEHEPS). The link for these REDCap surveys will be imbedded in Thinkific. A study team member will be available to assist in creation of the Thinkific account or completion of these initial surveys. Participants will leave their initial clinic appointment with a packet containing: a 3 pack of resistance bands, a copy of their consent form and a copy of the informational packet about the exercise program (see attached) that can otherwise be accessed through the Thinkific course.

Participants will additionally access the Thinkific account at home to complete an exercise based prehabilitation course. This course will provide video and written instruction on how to perform each exercise safely, as well as how to properly increase the intensity of the program, (e.g. resistance, number of repetitions and sets). This program will also include links to the American College of Surgeons alcohol related recommendations and the Maine QuitLink for tobacco/smoking and vaping cessation that patients may access if applicable. Participants will be instructed to perform daily exercise and keep track of their exercise in either a handwritten or electronic log (see attached document) until their surgery or until the final clinic visit if surgery is ultimately not performed. The log is available as a paper copy provided at the first visit and as a pdf embedded in the Thinkific course.

<https://mainehealth.thinkific.com/courses/prehab-exercise>

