Repeat self-administered survey with the SF-36 will become available through a direct email link from REDCap at two and four weeks after initiation of the prehabilitation program. If participants do not complete the surveys, they will receive a reminder email, generated automatically by REDCap, at 24 and 48hrs after the initial email was sent (please see attached screen shot of emails). At the final clinic visit prior to surgery, the participant's exercise log will be collected by the study team. The participant's exercise log will either be physically brought to clinic or uploaded by the participant through the Thinkific platform prior to this final appointment. Repeat frailty screening, with the RAI, will be performed by the surgical oncology clinic nursing staff at every follow up clinic appointment until surgery as part of the patients' normal care.

Participants will complete a final self-administered SF-36 survey and a survey to assess their satisfaction with the exercise prehabilitation program anytime during the week leading up to their surgery, or the week after their final appointment if they ultimately are not a surgical candidate. The link to this final REDCap survey is embedded in Thinkific. The surgeon will remind patients at their final clinic visit to complete these surveys.

During the extent of the study, if patients have questions pertaining to the study they will be able to contact their surgeon at any time by contacting the surgical oncology clinic. If the patient has questions or concerns related to the performance of the prehabilitation program exercises, they will be directed to a licensed physical therapist.

Please reference to the attached material to view each of the following surveys:

Risk Analysis Index (RAI):

The RAI is a validated frailty screening tool that was developed and implemented at the University of Nebraska. Components of the RAI include nursing home admission, unintentional weight loss, renal failure, congestive heart failure, poor appetite, gender, shortness of breath, malignancy, age, cognition, and activities of daily living.²⁰

36-Item Short Form Survey (SF-36):

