We believe that most individuals will benefit by participating in this study. Participants are likely to see improvements in strength and endurance to participation in a regular exercise program. Further, these improvements may help participants recovery from surgery. This pilot study would be the first step towards offering surgical patients what is becoming standard of care. The data collected will be used to benefit patients in the future. If the results of this pilot study support our hypothesis, it is likely the prehabilitation program will be implemented widely for surgical patients at MMC. This holds the potential for a large positive impact in the future by reducing negative post-surgical outcomes. This likely has the benefit of not only improved quality of life and functionality for the patient, but also decreased healthcare utilization and cost.

POTENTIAL PROBLEMS

- Loss to follow up: As a prospective study, patients enrolled may be loss to follow up. Some reasons include if a patient transitions care to a different provider or moves. The study team will make efforts to maintain all participant and will perform phone calls if needed to re-engage participants that may have been lost. (please see phone script)
- Technology: One of the inclusion criteria for this study is home internet access and established email account. Having these does not mean a participant will be proficient in using the internet. They may struggle to access or use the technology. To try and combat this, we have made care members easily available to answer questions and help participants trouble shoot.

TIMELINE

Because this intervention is recommended in most perioperative protocols, we hope to implement this program as soon as possible. Our goal is to recruit 20 patients within three months. Each patient will participate in the prehabilitation program for at least two weeks. It is

difficult to predict how long a patient will be in the program because the duration depends on when their surgery is eventually scheduled. This is individualized, and typically ranges from two weeks to six months. We hope to complete data collection in seven months. At that time, we hope to complete data analysis and submit an abstract by July, 2022.

REFERENCES

1. 2019 profile of older americans. In: Living USDoHaHSAoC, ed2019:5-6, 17-18.

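### Does the hoped-for seven months of data collection conflict with three months of recruitment and programs of up to six months?

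*Combined protocol and SAP*

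**What the plan says.** The figures come from the Timeline section of the combined protocol and SAP. On recruitment: "Our goal is to recruit 20 patients within three months". On time in the program, which the section calls hard to predict because it depends on the surgery date: "This is individualized, and typically ranges from two weeks to six months". On the end of collection: "We hope to complete data collection in seven months". On what comes next: "At that time, we hope to complete data analysis and submit an abstract by July, 2022".

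Study Population describes the path from first consultation to surgery and gives the same upper end: "This process can span anywhere from 4 weeks to 6 months". The lower ends differ (two weeks against four), but the lower end does not enter the sum at issue.

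Study Procedures sets each participant's own end point. Exercise and logging continue "until their surgery or until the final clinic visit if surgery is ultimately not performed". At the final clinic visit before surgery the "exercise log will be collected by the study team", although participants may upload it to the online platform before that visit. The last SF-36 and the satisfaction survey are completed in the week before surgery, "or the week after their final appointment if they ultimately are not a surgical candidate". Data Management has the linking master list deleted after data collection has been finalized, and gives no calendar date for that.

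**The concern.** Read as one schedule that starts at first enrollment, the three durations do not fit together: three months plus six is nine, not seven. Analysis is placed at the end of the seven months, the master list is deleted when collection is finalized, and no sentence says what happens to a participant still exercising at that point.

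If collection did stop at month seven, the end-of-program items would be at risk for late enrollees with long programs. These are the exercise log (adherence, aim 1a, and the outcome side of aim 1b), the satisfaction survey (aim 1c), and the final SF-36 and last RAI (aims 2a and 2b). The loss would depend on program length and would probably fall mainly on patients who have chemotherapy first. The adherence results would then describe mostly the shorter programs. Deleting the master list too early would also remove the planned means of linking a last survey to its participant.

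**Working it through.** **Inputs**
- Recruitment window: 3 months (Timeline, a goal).
- Time in program, D: 2 weeks (about 0.5 month) to 6 months (Timeline, typical range); 4 weeks (about 0.92 month) to 6 months (Study Population).
- Survey week after the final appointment: 1 week = 12/52 = 0.23 month, only for participants who are not surgical candidates (Study Procedures).
- Stated collection period: 7 months, start not given (Timeline).
- Planned enrollment: 20.

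**Can the stated seven months be reproduced?** Time needed = recruitment window + D (+ 0.23 without surgery).
- From first enrollment, longest typical program: 3 + 6 = 9 months; with the survey week, 9.23.
- From first enrollment, shortest program: 3 + 0.5 = 3.5 months.
- From the end of recruitment, longest typical program: 6 months; with the survey week, 6.23. Both fit within 7.

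So seven is not the sum of the other figures, and the section does not present it as one. Whether it is too short depends on a start point that is not stated.

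**What would seven months from first enrollment cover?** A program of length D fits if enrollment is no later than month 7 − D.
- D = 4: by month 3, so every participant fits.
- D = 5: by month 2.
- D = 6: by month 1.

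If accrual is even over 0 to 3 months (an assumption), the share unfinished at month 7 is max(0, (D − 4)/3): 0% at four months or less, 33% at five, 67% at six.

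**How many of 20?** The document gives no distribution of durations, so these are illustrations under even accrual:

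| Assumed duration, 0.5 to 6 months | Share unfinished at month 7 | Of 20 |
|---|---|---|
| Triangular, most programs short (mode 0.5) | 8/(9 × 5.5²) = 2.9% | 0.6 |
| Uniform | 2/(3 × 5.5) = 12.1% | 2.4 |
| Triangular, most programs long (mode 6) | 21.3% (simulation) | 4.3 |

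Uniform durations starting at 0.92 month give 2/(3 × 5.08) = 13.1%, or 2.6 of 20. With mostly short programs, the chance that even one participant runs past month 7 is about 45%.

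**What is in hand by month 7 in any case?** Baseline surveys, and the two- and four-week SF-36: for someone enrolled at month 3 the four-week survey falls at 3 + 0.92 = 3.9 months. A log already uploaded to the platform would be available too.

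**Is there a cut-off at month seven?** Taking the sections together: Study Procedures ends participation at surgery or the final visit and mentions no calendar date. Data Management ties deletion of the master list to an event, the finalizing of collection. Timeline places analysis at the point where collection is complete and expresses both as hopes. None of these tells the team to stop following anyone at month seven.

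**The case for a change.** The strongest case for a change is that the fix costs two or three sentences while the error it guards against is hard to undo. The document does not define when collection is finalized. A team working to the hoped-for dates could take month seven literally, delete the list and analyze without the longest programs, which a feasibility pilot should not under-represent. The only follow-up contingency, telephone calls in Potential Problems, is for participants who may be lost, not for those who are unfinished.

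Part of this stands. The start of the seven months is not stated, and no sentence says in so many words that collection ends with the last participant. Nine months from first enrollment is also the more cautious planning figure.

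The rest does not carry the point. The harm needs a cut-off that the document does not contain and that would contradict its own participant-level end points. When every participant is followed to surgery or the final visit, the ordinary meaning of finalized collection is that all of them have got there. A closing rule would write down what is already implied. An effect on the July 2022 abstract cannot be shown either, because no enrollment start date is given.

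**Conclusion.** The concern does not call for a change. The sum is right: counted from first enrollment, covering a six-month program begun at month 3 takes 9 months (about 9.2 without surgery), against a hoped-for 7. But that is the far end of a typical range combined with the last day of recruitment, not a certainty for 20 patients, and it disappears if the seven months start when recruitment ends.

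Followed as written, the plan keeps each participant to their own end point, so the consequence is at most a finish about two months later than hoped. The 0.6 to 4.3 of 20 who might be unfinished at month seven is a range under assumed accrual and duration shapes, and it counts people followed for longer, not people lost. No sample size, error rate, threshold or analysis method relies on the seven-month figure, and Data Analysis treats all comparisons as exploratory. This conclusion rests on reading finalized collection as the point when all participants have reached surgery or completed their final visit and surveys, which is what Study Procedures supports.
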